**Table 5-6: ADA Sample Status**

ADA sample status	Definition
ADA negative (ADA-)	Sample values that are either 'negative screen' or 'positive screen' and 'negative immuno-depletion' if corresponding rozanolixizumab concentrations are equal or below the validated drug tolerance limit of the ADA assay (200ug/ml rozanolixizumab) allowing detection of 100 ng/ml ADA. Note that if an ADA sample does not have a corresponding PK sample (at the same visit), then it is assumed that the drug concentration is below the drug tolerance limit.
ADA positive (ADA+)	Sample values that are 'positive screen' and 'positive immuno-depletion'
ADA inconclusive	Sample values that are either 'negative screen' or 'positive screen' and 'negative immuno-depletion' but with corresponding rozanolixizumab concentrations above the validated drug tolerance limit of the ADA assay (200ug/ml rozanolixizumab) allowing detection of 100 ng/ml ADA.

ADA sample status	Definition
	Note that if an ADA sample does not have a corresponding PK sample (at the same visit), then it is assumed that the drug concentration is below the drug tolerance limit and therefore this sample cannot be classified as 'Inconclusive'.
Missing	Samples that were collected per schedule but could not be tested for ADA status due to inadequate sample volume, mishandling, or errors in sample collection, processing, storage, etc.
Evaluatable ADA sample	A sample for which the sample status is not missing nor ADA inconclusive

Neutralizing antibody (NAb) sample status (positive/negative/inconclusive/missing) will be determined for ADA positive samples. Samples that are NAb positive will be evaluated in a titration assay to quantify the NAb level and will be reported as titer.

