#### ADA/NAb Participant Status

The ADA/NAb participant status will be further classified on study participant level as outlined below (Shankar et al. 2014; Rup et al. 2015, Presentation Immunogenicity Summit, 2021, Joleen White, Enabling Clinical Immunogenicity Impact Assessment with Standardized Data Tabulation Models).

The by-participant classifications for ADA status will be derived 3 times:

- For the entire study duration (ie, including all samples from Treatment Periods 1 and 2, and SFU). Note that participants in Sequence 2 will not have samples from Treatment Period 1.
- Based on RLZ 12 weeks exposure:
  - Sequence 1 Baseline (Visit 3) to Day 85 (Visit 15)
  - Sequence 2 Baseline (Visit 15) to Day 169 (Visit 27)
- Based on RLZ 24 weeks exposure:
  - Sequence 1 Baseline (Visit 3) to Day 169 (Visit 27)

Based on the above, participants in Sequence 1 will have 3 ADA classifications, and participants in Sequence 2 will have 2 ADA classifications. The combined ADA/NAb participant status will be derived only based on the ADA status for the entire study duration (ie, each participant will have only 1 ADA/NAb classification).

The ADA participant status is composed of 6 individual categories: ADA negative, inconclusive, and ADA positive whereby a positive participant's status is further subdivided into treatment-induced, treatment boosted, or non-treatment-emergent ADA positive.

However, the ADA participant status as defined in category 1 (ADA-NEG) can only be applied for participants having 2/3 (66.6%) of the protocol scheduled post-baseline ADA samples 'evaluable', (ie, neither missing as per schedule nor inconclusive) which is equivalent to the following:

- For the entire study duration
  - For Sequence 1, a minimum of 6/8 samples
  - For Sequence 2, a minimum of 4/5 samples
- RLZ 12 weeks
  - For Sequence 1, a minimum of 2/3 samples
  - For Sequence 2, a minimum of 2/3 samples
- RLZ 24 weeks
  - For Sequence 1, a minimum of 4/6 samples

Study participants that have a positive baseline value and no post-baseline values collected will be categorized as categories 2 (ADA-POS) and 5 (Non-TE-POS).

For a dropout participant, the participant status would be evaluated on the basis of the sample collection compared to all anticipated protocol scheduled samples assuming that they had actually completed the study.

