**Table 5-7: ADA Participant Status Categories**

Term	Definition	Category
ADA participant status categories		
ADA-NEG (Pre ADA negative – treatment induced ADA negative)	Study participants who have negative ADA sample status at baseline and at all sampling time points post-baseline with the number of evaluable samples (non- missing per schedule nor inconclusive) more or equal to 2/3 as defined above.  [Note: study participants with baseline samples missing and negative ADA status at all sampling time post-baseline are included in this category; based on the following rationale: in case the participant would be pre-Ab positive, the participant is expected to present ADA positive samples post-baseline]	1
ADA-POS	Study participants who have a positive ADA sample status at any time point (either Baseline, or post-Baseline)	2

Term	Definition	Category
TI-POS (Pre ADA negative – Treatment Induced ADA positive)	Study participants who have a negative ADA status at baseline and positive ADA status at any sampling point post-Baseline.	3
TB-POS (Pre ADA positive – Treatment Boosted ADA positive)	Study participants who have a positive ADA status at baseline and positive ADA status at any sampling point post-baseline with non-missing increased titer values compared to baseline (>fold difference from Baseline value as determined by the MSR of the assay).	4
Non-TE-POS (Pre-ADA positive- Non-Treatment - Emergent ADA positive)	Study participants who have a positive ADA status at baseline and 1) negative ADA status at all evaluable sampling points post-baseline or 2) positive ADA status at any evaluable sampling points post- baseline with non-missing titer values of the same or lower magnitude as baseline ( $\leq$ fold difference from Baseline value as determined by the MSR of the assay).	5
Inconclusive	Study participant for who the ADA participant status cannot be defined due to missing or inconclusive samples. Inconclusive [1]: Study participant that had negative ADA status at baseline and post-baseline samples missing per schedule or inconclusive that is higher than the % allowed as defined above, while others post-baseline samples are ADA negative up to the time point of interest. Inconclusive [2]: Participants who do not satisfy any of the above criteria.	6
Combined ADA participant status categories		
TE-POS (TE ADA positive)	Includes study participants defined in category 3 and 4	7

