Treatment emergent ADA positive – NAb positive (TE-POS, NAb-POS)	Study participants in category 7 who have at least one NAb positive sample	8
Treatment emergent ADA positive – NAb negative (TE-POS, NAb-NEG)	Study participants in category 7 who have no NAb positive samples	9
Non-treatment emergent ADA positive – NAb positive (Non-TE-POS, NAb-POS)	Study participants in category 5 who have at least one NAb positive sample	10
Non-treatment emergent ADA positive – NAb negative (Non-TE-POS, NAb-NEG)	Study participants in category 5 who have no NAb positive samples	11

The fold difference increase from baseline value, ie, the minimum significant ratio (MSR) determined during assay validation, will be reported in the relevant tables, listings and figures. It reflects the fold difference in titer level that considered higher than the assay variation in titer determination.

Calculation of Fold Increase for use of MSR, and for classifying ‘Non-TE-POS (Pre-ADA positive- Non-Treatment-Emergent ADA positive)’ and ‘TB-POS (Pre ADA positive – Treatment Boosted ADA positive)’ category:

Fold increase= post-dose titer/baseline titer

The following summaries, figures and listings will be produced and will be presented using the SS-r:

Tables:

- Summary table displaying the number and percentage of study participants with a positive ADA, negative ADA, inconclusive or missing ADA sample status at the time of each visit by planned treatment sequence.
- Summary table displaying the number and percentage of study participants with a positive NAb, negative NAb, inconclusive or missing NAb sample status at the time of each visit by planned treatment sequence.
- Number and percentage of study participants in each of the individual and combined ADA participant status categories and combined categories (1-11) presented in [Table 5-7](#) for each time period specified above. The denominator will be the total number of study participants with an individual ADA participant category defined for each time period.
- Total prevalence of pre-existing ADA and NAb, defined as number and percentage of participants having an ADA/NAb positive sample status at baseline, with the denominator being the total number of study participants having an evaluable ADA/NAb sample result at baseline.

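### SAP Table 5-7 labels an ADA-positive participant with no evaluable NAb result as NAb negative, so the NAb-negative groups can include participants of unknown status

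*SAP*

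**What the plan says.** At sample level (SAP 5.7, text after Table 5-6): "Neutralizing antibody (NAb) sample status (positive/negative/inconclusive/missing) will be determined for ADA positive samples".

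At participant level (SAP Table 5-7), NAb status has two outcomes only:

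- Category 8 (treatment-emergent, NAb positive): "Study participants in category 7 who have at least one NAb positive sample".
- Category 9 (treatment-emergent, NAb negative): "Study participants in category 7 who have no NAb positive samples".
- Categories 10 and 11 apply the same split to non-treatment-emergent positives. Category 11 is "Study participants in category 5 who have no NAb positive samples".

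ADA status is handled differently. The ADA-negative label "can only be applied for participants having 2/3 (66.6%) of the protocol scheduled post-baseline ADA samples" evaluable. There is also a separate inconclusive group, category 6: "Study participant for who the ADA participant status cannot be defined due to missing or inconclusive samples".

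For the table of categories 1 to 11, the SAP fixes the percentage base: "The denominator will be the total number of study participants with an individual ADA participant category defined for each time period". A further table counts participants with "positive NAb, negative NAb, inconclusive or missing NAb sample status at the time of each visit by planned treatment sequence".

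**The concern.** Categories 9 and 11 rest on the absence of a positive result, not on the presence of a negative one. With four possible sample statuses, these are not the same thing. A participant who is ADA positive, and for whom the NAb assay gave nothing usable, is reported as though neutralizing activity had been looked for and not found.

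The NAb-negative label is then used as a grouping variable. Under SAP 5.7, categories 8 to 11 define the groups in the ADA titer box plot. With categories 1 and 6, they also define the BPI-SF interference time course. Categories 8 and 9, with 1 and 6, define the spaghetti plots of percentage change in total IgG. These figures are where a reader would look for a weaker IgG or pain response in NAb-positive participants. If the NAb-negative group contains some participants of unknown status, that contrast may be blurred. The groups will be small: Sequence 3 is left out of the immunogenicity analysis, which leaves a planned 20 + 20 = 40 participants before any restriction to ADA positives.

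**Working it through.** **1. Inputs.** The plan states no NAb incidence, so there is no NAb figure to reproduce. The check is one of logic, followed by an illustration on assumed counts.

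**2. The ADA rule works as stated.** The SAP's minimum numbers of evaluable ADA samples follow from rounding 2/3 × n up to a whole sample:

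| Period and sequence | n scheduled | 2/3 × n | Minimum | SAP states |
|---|---|---|---|---|
| Entire study, Sequence 1 | 8 | 5.33 | 6 | 6 |
| Entire study, Sequence 2 | 5 | 3.33 | 4 | 4 |
| 12 weeks, Sequence 1 or 2 | 3 | 2 | 2 | 2 |
| 24 weeks, Sequence 1 | 6 | 4 | 4 | 4 |

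SAP 5.7 sets no such minimum for NAb.

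**3. Where an unevaluated participant goes.** Categories 8 and 9 are exact complements within category 7, and categories 10 and 11 within category 5. Take a category 7 participant whose ADA-positive samples all have NAb status inconclusive or missing. There is no NAb-positive sample, so category 8 does not apply and category 9 does. Category 6 cannot take this participant, because it concerns ADA status, which is already settled as category 3 or 4.

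**4. A case the SAP itself creates.** Under ADA/NAb Participant Status, a participant with a positive baseline ADA sample and no post-baseline sample is placed in categories 2 and 5. NAb status then rests on one sample. If that result is missing, Table 5-7 gives category 11, NAb negative.

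**5. Effect on the counts.** Let N be the participants with an ADA category, T those in category 7, n8 those in category 8, and m those in category 7 with no evaluable NAb result.

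- Category 9 as written: T − n8.
- Category 9 requiring an evaluable result: T − n8 − m.
- Category 8, either way: n8, reported as n8/N.
- Range for NAb positives, given m unknowns: n8/N to (n8 + m)/N.

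**6. Illustration.** Assume N = 40 (all planned participants in Sequences 1 and 2), T = 10 and n8 = 3. None of these except the planned 40 comes from the documents.

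| m | Category 9 as written | Category 9 as corrected | Category 8, both | Upper end for NAb positive |
|---|---|---|---|---|
| 0 | 7/40 = 17.5% | 7/40 = 17.5% | 3/40 = 7.5% | 3/40 = 7.5% |
| 1 | 7/40 = 17.5% | 6/40 = 15.0% | 3/40 = 7.5% | 4/40 = 10.0% |
| 2 | 7/40 = 17.5% | 5/40 = 12.5% | 3/40 = 7.5% | 5/40 = 12.5% |
| 3 | 7/40 = 17.5% | 4/40 = 10.0% | 3/40 = 7.5% | 6/40 = 15.0% |

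The category 9 count falls by m. The category 8 count and percentage do not move. With m = 0 nothing changes.

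**The case against.** Four points can be made for the plan as it stands.

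*The NAb-positive percentage is not altered.* A reader might infer that neutralizing incidence is understated, for example by comparing 3/10 = 30% with 3/9 = 33% or 3/7 = 43% among evaluable treatment-emergent positives. The documents do not support that reading. The SAP's percentage base is everyone with an ADA category, not category 7 and not NAb-evaluable participants, so the category 8 and 10 figures are the same under either definition. They are lower bounds when unknowns exist, and nothing more can be said. This point stands.

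*The trigger is narrow.* All of a participant's ADA-positive samples must lack a usable NAb result, and SAP 5.7 says every confirmed ADA-positive sample will be assayed. This stands as a limit on likely size. It does not rule the case out, because the SAP itself lists inconclusive and missing as outcomes, and protocol 9.4.2.2 allows NAb characterization of only a subset of ADA-positive samples.

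*Unknown results remain visible.* The by-visit NAb table and the listings show inconclusive and missing results, and baseline NAb prevalence uses an evaluable denominator. This is true, but none of it changes a participant's category or group in a figure.

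*The SAP elsewhere accepts some missing data as negative.* A missing ADA baseline with negative post-baseline samples counts as ADA negative, and a missing PK sample is taken to be below drug tolerance. So the contrast with the ADA rules is not absolute. Even so, the missing-baseline rule comes with a stated rationale and observed negative samples. Categories 9 and 11 have neither.

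**Conclusion.** The rule is wrong as written: it can label a participant NAb negative with no negative NAb result on record. The error has one direction. The category 9 and 11 counts can only be too high or correct.

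Its size cannot be computed from the documents. It equals the number of category 7 and category 5 participants with no evaluable NAb result, and is zero if there are none. In the assumed example, one to three such participants reduce the shown-negative count from 7 to between 6 and 4.

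The reach is limited to the category 9 and 11 rows and the three kinds of descriptive figure named above. The SAP tables of IgG and BPI-SF change by ADA status use categories 1 to 6, and the adverse-event tables by ADA status use categories 1, 5, 6 and 7, so none of these depends on the NAb split. The primary, secondary and main safety analyses are unaffected, and the SAP plans no formal hypothesis testing. This is a classification error in an exploratory analysis, worth correcting because the correction is simple.

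**What to change.** In SAP Table 5-7:

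1. Define categories 9 and 11 as having no NAb-positive sample and at least one evaluable NAb result, with all evaluable results negative. State that evaluable means neither missing nor inconclusive, as Table 5-6 already does for ADA samples.
2. Add a NAb inconclusive/missing category for both treatment-emergent and non-treatment-emergent ADA positives, for participants who meet neither the positive nor the negative definition.
3. Show that category wherever categories 8 to 11 are used: the category table, the ADA titer box plot and the BPI-SF time course. In the IgG spaghetti plots, which use categories 8 and 9, show the treatment-emergent one.
4. Give the number of NAb-evaluable participants beside the category 8 to 11 counts, so that the category 8 and 10 figures can be read as lower bounds where unknowns exist.

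The cost is SAP wording, one extra category in programming (for each ADA-positive group) and the matching table and figure shells. No new data are needed. The change is best made before unblinding, so that it is not a post-hoc reclassification.

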Anti-drug antibody (ADA)	
Baseline is defined as the last measurement prior to receiving the first dose of rozanolixizumab. For participants randomized to Sequence 1, Baseline is the Day 1 (Visit 3, Week 1) pre-dose assessment, or Day -7 (Visit 1, Week -1), if missing. For participants randomized to Sequence 2, Baseline is the Day 85 (Visit 15, Week 13) pre-dose assessment, or Day 1 (Week 3, Visit 1), if missing.
 
Note that if a dose of study medication was not received at Visit 3, or Visit 15 (dependent upon the participant), but the ADA assessment was performed at Visit 3 or Visit 15, this assessment would still be used as the Baseline assessment.

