- The first occurrence of treatment-emergent ADA positivity: cumulative number and percentage of TE-ADA positive participants (category 7) who are ADA positive for the first time based on samples collected over the entire study duration, including SFU.
- Summary table of mean maximum percentage change from Baseline in total IgG summarized by ADA participant categories (1-6) for the following:
  - Sequence 1, Treatment Period 1 (RLZ 12 weeks) using ADA participant category based on RLZ 12 weeks exposure and maximum percent change from Baseline in total IgG in Treatment Period 1.
  - Sequence 2, Treatment Period 2 (RLZ 12 weeks) using ADA participant category based on RLZ 12 weeks exposure and maximum percent change from Baseline in total IgG in Treatment Period 2.
  - Sequence 1, Treatment Period 1 and Treatment Period 2 (RLZ 24 weeks) using ADA participant category based on RLZ 24 weeks exposure and maximum percent change from Baseline in total IgG in Treatment Period 2

- Sequence 1 Treatment Period 1 and Sequence 2, Treatment Period 2 (RLZ 12 weeks) using ADA participant category based on RLZ 12 weeks exposure and maximum percent change from Baseline in total IgG in Treatment Period 1 for Sequence 1, and Treatment Period 2 for Sequence 2.
- Summary table of mean change from Baseline in BPI-SF Interference score in Treatment Periods 1 and 2, summarized by ADA participant categories (1-6) for the following:
  - Sequence 1, Treatment Period 1 (RLZ 12 weeks) using ADA participant category based on RLZ 12 weeks exposure and change from Baseline in BPI-SF interference score at Visit 15.
  - Sequence 2, Treatment Period 2 (RLZ 12 weeks) using ADA participant category based on RLZ 12 weeks exposure and change from Baseline in BPI-SF interference score at Visit 27.
  - Sequence 1, Treatment Period 1 and Treatment Period 2 (RLZ 24 weeks) using ADA participant category based on RLZ 24 weeks exposure and change from Baseline in BPI-SF interference score at Visit 27.
  - Sequence 1 Treatment Period 1 and Sequence 2, Treatment Period 2 (RLZ 12 weeks) using ADA participant category based on RLZ 12 weeks exposure and change from Baseline in BPI-SF interference score at Visit 15 for Sequence 1, and Visit 27 for Sequence 2.
- Overall summary table of TEAEs summarized by ADA participant categories 1, 5, 6, and 7 where the participant category is based on ADA data for the entire study duration. This table will include the following:

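### SAP 5.7: the table of first treatment-emergent ADA has no titer condition, so it can date treatment-boosted participants before their titer rises

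*SAP*

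**What the plan says.** The list of tables in SAP Section 5.7 includes one introduced as "The first occurrence of treatment-emergent ADA positivity". Its content is defined as the "cumulative number and percentage of TE-ADA positive participants (category 7) who are ADA positive for the first time", using samples from the whole study with safety follow-up included. The definition contains no titer threshold and does not say whether Baseline samples count.

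Table 5-7 supplies the categories:

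- Category 7 (TE-POS): "Includes study participants defined in category 3 and 4".
- Category 3 (TI-POS): "Study participants who have a negative ADA status at baseline and positive ADA status at any sampling point post-Baseline".
- Category 4 (TB-POS): "Study participants who have a positive ADA status at baseline and positive ADA status at any sampling point post-baseline with non-missing increased titer values". The increase must exceed the MSR.

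Table 5-2 fixes the reference sample: "Baseline is defined as the last measurement prior to receiving the first dose of rozanolixizumab". That is the Visit 3 pre-dose sample in Sequence 1 and the Visit 15 pre-dose sample in Sequence 2. The text after Table 5-7 defines fold increase as post-dose titer over Baseline titer. It gives the purpose as separating TB-POS from participants who are positive at Baseline without a boost. It does not use fold increase to date onset.

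**The concern.** The heading of the table and its counting rule describe different events for one of the two groups counted. For TI-POS, the first positive sample is the treatment-emergent event. For TB-POS, positivity existed before rozanolixizumab, and the treatment-emergent feature is the later titer rise. A rule that looks for the first positive sample dates positivity rather than emergence.

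If it is programmed as written, the cumulative curve for treatment-emergent ADA can rise too early, and readers would take pre-existing antibody for early emergence on drug. The protocol's exploratory objective covers the incidence and emergence of ADA, and in the SAP's table list this is the table described as showing first occurrence.

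**Working it through.** The documents give no figure for this point, so the check is logical, followed by two illustrations.

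**Inputs.** Category definitions from Table 5-7; Baseline from Table 5-2; scheduled post-Baseline ADA samples over the entire study from SAP 5.7 (8 in Sequence 1, 5 in Sequence 2); visit days from the protocol's Schedule of Activities (Visit 3 = Day 1, Visit 4 = Day 8, Visit 23 = Day 141).

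**Step 1: possible TB-POS records.** Baseline is positive. Let each post-Baseline sample be negative (N), positive at or below the MSR (P), or positive above it (B), with at least one B. For k samples there are 3^k − 2^k patterns:

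- Sequence 1: 6561 − 256 = 6305
- Sequence 2: 243 − 32 = 211

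**Step 2: Baseline samples included.** The first positive sample is no later than Baseline in every pattern: 6305 of 6305 and 211 of 211.

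**Step 3: post-Baseline samples only.** The first positive sample is also the first boosted one when the first non-negative result is B, which happens in (3^k − 1)/2 patterns. In the remainder a P comes first and onset is dated too early.

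| | Dates coincide | Dated before the boost |
|---|---|---|
| Sequence 1 | 3280 (52%) | 3025 (48%) |
| Sequence 2 | 121 (57%) | 90 (43%) |

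These are counts of possible patterns, not probabilities.

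**Step 4: size in days (constructed example).** Take a Sequence 1 participant, positive at Baseline, with an unchanged titer at Visits 4, 11, 15 and 16 and the first rise above the MSR at Visit 23.

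- Baseline included: 141 − 1 = 140 days early
- Post-Baseline only: 141 − 8 = 133 days early

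**Step 5: effect on the table (assumed data).** Take three TI-POS participants first positive at Visits 15, 23 and 27, and two TB-POS participants first boosted at Visits 23 and 27. For the middle row, both TB-POS participants are also assumed positive at Visit 4 without a boost. Cumulative counts:

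| Rule | Baseline | V4 | V11 | V15 | V16 | V23 | V27 |
|---|---|---|---|---|---|---|---|
| First positive, Baseline included | 2 | 2 | 2 | 3 | 3 | 4 | 5 |
| First positive, post-Baseline only | 0 | 2 | 2 | 3 | 3 | 4 | 5 |
| TB-POS dated by boost | 0 | 0 | 0 | 1 | 1 | 3 | 5 |

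The final total is 5 under every rule; only the timing moves.

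**The case against.** The best defense is that the heading governs. It names treatment-emergent positivity, and Table 5-7 makes a rise above the MSR the treatment-emergent feature of TB-POS, so a careful programmer would date by the boost. That is a sensible guess at the intent, but the definition under the heading asks only for a first positive sample. It does not remove the mismatch.

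A reader might go further and infer that every TB-POS participant will be dated before any rozanolixizumab. The documents do not settle that:

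- SAP 5.7 tabulates Baseline positivity separately, as pre-existing ADA.
- It describes the entire study duration as samples from Treatment Periods 1 and 2 and safety follow-up, and says that Sequence 2 has no Treatment Period 1 samples.
- SAP 5.1.1.2 assigns post-Baseline measurements up to Visit 15 to Treatment Period 1. It names efficacy, PK and PD but not ADA. Carried over to ADA, it would leave the Baseline samples out.

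Against this, the cumulative rule for the IgG plots in the same section counts any positive sample from ADA Baseline onward. Both readings are open. Excluding Baseline narrows the problem to TB-POS participants with an unboosted positive sample before the boost, but does not remove it.

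A reader might also infer that readings of ADA against IgG or efficacy are distorted. They are not. The IgG and BPI-SF tables use participant categories, the IgG plots have their own cumulative rule, and none takes onset from this table. The protocol endpoint is ADA incidence at scheduled assessments, which other tables serve. Individual titer plots for categories 3 to 5 and a by-visit listing of fold change would let a reader recover the boost date.

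**Conclusion.** The point holds, and it is minor. As worded, the table uses a rule that is right for TI-POS and lacks the titer condition that defines emergence for TB-POS. On either reading of which samples count, it can place a TB-POS onset before the boost; placement before exposure follows only if Baseline samples are included. The 133 to 140 days comes from a deliberately unfavorable record and is not an expected error.

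The consequence is confined to visit timing in one descriptive, exploratory table. Category membership, final cumulative totals, IgG plots and efficacy analyses are unaffected. The documents do not give the number of TB-POS participants, and if there are none the table is correct as written.

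**What to change.** Add an onset rule to this table in SAP 5.7:

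- TI-POS: the first ADA-positive post-Baseline sample.
- TB-POS: the first post-Baseline sample whose fold increase over Baseline titer is greater than the MSR.
- Start the cumulative display at the first post-Baseline visit.

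Every category 3 or 4 participant has at least one qualifying sample by definition, so the rule always returns a date. The cost is one sentence and one derivation. Fold increase is already computed for Table 5-7 and fold change is already listed by visit, so no new data are needed.
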